- **PHASE 4: Conduct a parallel group randomized trial.** Randomize 252 college students with ADHD to: (1) VR environment alone, (2) VR + contingency management or (3) a pass-through VR headset for 6 weeks. Assess target mechanisms at each session and collect ratings of functioning at baseline, intervention outcome and at a 3-month follow-up to facilitate evaluation of efficacy, dose, moderation, and mediation.

All visits will be conducted at participants' homes and the LSU or Rutgers library, [name] lab at Louisiana State University, or via HIPAA-compliant videoconferencing (e.g., Zoom). Trained study staff will be on-site and available to assist at all times.

A. Research Procedures

This study is taking place at two sites, Rutgers and Louisiana State University (LSU). Rutgers is the "Psychology site" and the PI is a licensed clinical psychologist, and LSU is the "Engineering/VR site" and the PI is in Computer Science. As such, all participant consenting, inclusion/exclusion evaluations, and outcome assessments are handled by the Rutgers site. These portions will be done virtually, via REDCap surveys and teleconference. Approximately half of the participants will be enrolled and use VR at the Rutgers site and half at the LSU site. The scheduling and implementation of the VR sessions is handled by the site/university where participants are located. All data are collected via REDCap and stored at the Rutgers site only. The only exception is the data captured by the VR (keyboard and mouse click data, eye gaze, and screenshot captures), which is maintained and analyzed at LSU.

For the VR intervention provided in each phase, participants will be provided the option of using the VR headset while completing homework and studying either in their rooms/homes or at the library, and at a consistent time each day to help control for natural variations in focus due to chronobiological sleep/wake preferences.

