VR intervention: After completing the initial evaluation and confirming eligibility, a new sample of 45 participants will be randomized to 1 of 3 groups and then scheduled to use the VR headset in their room/home or the library. Randomization will be performed (1:1:1) to the three conditions. Randomization will be blocked on ADHD medication status to ensure an equal number of participants taking and not taking ADHD medication in each group. Phase 3 includes a 2-session baseline where all participants complete homework and study outside of VR (total of 12 sessions; 2 non-VR baseline and 10 in VR condition). During each session, participants will complete a set of standardized reading comprehension problems to determine how many they complete and how accurately. LSU and Rutgers study staff will run VR intervention visits at their respective study sites.

Group 1, VR passthrough: After completing the two session non-VR baseline, participants will use the VR headset in their room/home or the library 10 times over three weeks (max twice a day with a minimum 2-hour break) for 1-hour sessions each time. The participant will wear the headset, but it will not be used as usual. The headset will be in “VR passthrough” mode, meaning the participant will see through to the normal environment and laptop (i.e., they can see the real world around them, just wearing a headset).

Group 2, VR environment only: After completing the two session non-VR baseline, participants will use the VR headset in their room/home or the library 10 times over three weeks (max twice a day with a minimum 2-hour break) for 1-hour sessions each time. The participant will wear the VR headset and engage in homework in the VR environment.

Group 2, VR environment + contingency management: After completing the two session non-VR baseline, participants will use the VR headset in their room/home or the 10 times

over three weeks (max twice a day with a minimum 2-hour break) for 1-hour sessions each time. The participant will wear the VR headset and engage in homework in the VR environment while receiving contingency management (real-time feedback on performance through red or green light FlowLight icon).

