- Service Utilization for College Students
- Current Day Medication Adherence survey
- BAARS-Self
- Pre-screening questions
- Adult Concentration Index (ACI)
- GAD-7
- PHQ-9
- Columbia Suicide Severity Index
- WHODAS (Required by NIMH/NDA)
- DSM-5 Level 1 Cross-Cutting Symptom Measure (Required by NIMH/NDA)
- BDEFS – Short Form
- BFIS
- Baseline Homework Motivation Index
- Baseline Homework Effort Index
- Academic Record (GPA & Percentage of Assignments Completed)
- Reading Comprehension Standardized Assessment
- SCID-V RV

Each of 10 sessions:

- Key strokes and mouse clicks
- Reading Comprehension Standardized Assessment
- Periodic screenshots of participant screens
- 10-item Systems Usability Scale (Sessions 4 and 10 only)
- Adult Concentration Inventory
- Homework Motivation Index
- Homework Effort Index
- Current Day Medication Adherence

Outcome Assessments:

- Current Day Medication Adherence survey
- BAARS-Self
- BDEFS – Short Form
- BFIS
- Academic Record (GPA & Percentage of Assignments Completed)
- Feasibility and usability of the VR systems

3-Month Follow-Up

- Current Day Medication Adherence survey
- BAARS-Self
- BDEFS – Short Form
- BFIS
- Academic Record (GPA & Percentage of Assignments Completed)
- Feasibility and usability of the VR systems

C. Study Duration

PHASE 1:

Each participant will be involved for approximately 4 weeks (1 week of initial evaluation, 2 weeks of intervention, 1 week of outcome assessment).

The initial evaluation will take approximately 1.5 hours.

Each VR intervention session will take approximately 1 hour (10 minutes of reading comprehension questions, 40 minutes of intervention, 10 minutes to complete surveys). Across the intervention, they will complete 10 1-hour sessions.

The outcome assessment will take approximately 30 minutes to complete, and the follow-up phone interview with the research team should take 15 minutes.

PHASE 2:

Each participant will be involved for approximately 5 weeks (1 week of initial evaluation, 2 weeks of intervention, 1 week of outcome assessment, 1 week of focus group).

The initial evaluation will take approximately 1.5 hours.

Each VR intervention session will take approximately 1 hour (10 minutes of reading comprehension questions, 40 minutes of intervention, 10 minutes to complete surveys). Across the intervention, they will complete 10 1-hour sessions.

The outcome assessment will take approximately 30 minutes to complete.

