analyzed using MPlus will address missing data using full information maximum likelihood estimates. This approach makes full use of available data and is one of several procedures considered the state of the art for addressing missing data.

Intent to Treat Analysis: An intent-to-treat approach will be used to analyze the data, wherein each participant will be kept in the group to which they were randomized for analysis, regardless of treatment compliance. A mixed-effects model will be used to account for the repeated-measure nature of the study design. Time will be treated as a dummy-coded categorical variable using baseline as the reference. A student-level random effect will be included and modeled using an auto-regressive covariance structure to account for within-subject dependence due to repeated measurements. The models will also include treatment condition as a student-level fixed effect, and condition x time interaction effects. This modeling will allow us to compare baseline to 8-week (post) changes, and the extent to which these changes differ across conditions.

Mediator Analyses: Mediational analyses will be conducted using structural equation modeling. There are advantages of a structural equation modeling approach to estimating and determining the significance of indirect effects within mediational models and outlined specific estimation procedures that are available in MPlus. All analyses will be conducted in MPlus which provides estimates that partition the total effect of an independent variable on a dependent variable into the direct and indirect effects using bootstrap estimation procedures. Preliminary analyses will be conducted separately for each mediator. Scores on the mediator will be modeled as a function of pretest scores on the mediator, intervention condition, and covariates. The intervention's effect can then be partitioned into the direct effect on changes (e.g., on school grades) at posttest and follow-ups and the indirect effects via the mediator. These initial analyses will be used to guide a more comprehensive model that will incorporate mediators that emerge as significant within the individual models. Primary mediation analyses will focus on whether change in the proposed mechanisms of action mediates improvement in AIM total scores and BDEFS.

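### For the three-visit Phase 4 ratings (BAARS, BDEFS, BFIS), the efficacy model tests raw change from baseline; this is valid, but adjusting for the pre-randomisation score would generally be more precise

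*Combined protocol and SAP*

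**What the plan says.** Section 6.1, Intent to Treat Analysis, sets out a mixed model for Phase 4. On time: "Time will be treated as a dummy-coded categorical variable using baseline as the reference". On the fixed effects: "The models will also include treatment condition as a student-level fixed effect, and condition x time interaction effects". On the aim: "This modeling will allow us to compare baseline to 8-week (post) changes, and the extent to which these changes differ across conditions". That paragraph does not list the outcomes the model is for. The Phase 4 paragraph before it mentions baseline covariates but names none for the efficacy model; the only rule given is to add those found to be associated with missing data.

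Section 1.3 says that Phase 4 will "collect ratings of functioning at baseline, intervention outcome and at a 3-month follow-up to facilitate evaluation of efficacy, dose, moderation, and mediation". In the Phase 3 and 4 schedule (Section 1.3 B), BAARS-Self, the BDEFS short form and BFIS appear at the initial evaluation, at the outcome assessment and under "3-Month Follow-Up".

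The initial evaluation comes before allocation. Section 1.3 A says for Phase 3: "After completing the initial evaluation and confirming eligibility, a new sample of 45 participants will be randomized to 1 of 3 groups". Phase 4 follows the same procedures with 252 participants. Randomisation is blocked on ADHD medication status.

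Adjustment for a pretest score does occur in the plan, but only in the mediation models: "Scores on the mediator will be modeled as a function of pretest scores on the mediator, intervention condition, and covariates".

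**The concern.** With baseline as one of the responses, a free condition effect and condition-by-time terms, each arm has its own baseline mean. The condition-by-time coefficient at post is then the difference between arms in mean change from those arm-specific baselines. Randomisation makes the true baseline means equal, so estimating them separately carries chance baseline differences into the contrast in full. A baseline-adjusted analysis removes only the share that the correlation justifies.

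What is at stake is precision on the two comparisons planned at d = 0.4 in Section 1.5: VR environment alone against pass-through, and against VR plus contingency management. The score needed for the adjustment is already collected.

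**Working it through.** **Inputs from the documents.** 84 per arm; d = 0.4 for the two comparisons above and d = 0.8 for VR plus contingency management against pass-through (Section 1.5). Model terms as quoted.

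**Assumed, because the documents do not give them.** Two-sided alpha of 0.05; no attrition; baseline-to-post correlation r of 0.3, 0.5 or 0.7; k = baseline SD / post SD; d expressed on the post SD.

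**The plan's own figure.** Section 1.5 gives 84 per arm without alpha or target power. For an outcome with unit SD, 84 per arm gives 73.1% power at d = 0.4 and 99.9% at d = 0.8 (noncentral t). By the normal approximation, 80% power at d = 0.4 needs 99 per arm two-sided or 78 one-sided. Neither is 84, so the figure can be neither confirmed nor refuted.

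**What the planned model estimates.** In 3,000 simulated trials (three arms, three visits, 84 per arm, complete data, r about 0.51), the condition-by-time estimate at post equalled the raw difference in mean change, with a largest discrepancy of 9e-16.

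**Variances, per participant, with post SD = 1.**
- Planned (raw change): 1 + k² − 2rk. With k = 1 this is 2(1 − r).
- Baseline-adjusted: 1 − r².
- Planned minus adjusted: (k − r)². This is never negative and is zero only when k = r.
- Ratio adjusted/planned: (1 − r²)/(1 + k² − 2rk). With k = 1 this is (1 + r)/2.

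**Power.** Effective d = 0.4/√variance, noncentrality = effective d × √(84/2), with 166 df (planned) or 165 df (adjusted). Example at r = 0.5, k = 1: planned 0.4/√1.00 = 0.400, noncentrality 2.59, power 73.1%; adjusted 0.4/√0.75 = 0.462, noncentrality 2.99, power 84.5%.

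| k | r | Planned variance | Adjusted variance | Ratio | Planned power | Adjusted power |
|---|---|---|---|---|---|---|
| 1.0 | 0.3 | 1.40 | 0.91 | 0.650 | 58.6% | 77.1% |
| 1.0 | 0.5 | 1.00 | 0.75 | 0.750 | 73.1% | 84.5% |
| 1.0 | 0.7 | 0.60 | 0.51 | 0.850 | 91.4% | 95.0% |
| 0.8 | 0.3 | 1.16 | 0.91 | 0.784 | 66.7% | 77.1% |
| 0.8 | 0.5 | 0.84 | 0.75 | 0.893 | 80.3% | 84.5% |
| 0.8 | 0.7 | 0.52 | 0.51 | 0.981 | 94.7% | 95.0% |

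**Equivalent sample size (k = 1).** To match the adjusted analysis at 84 per arm, the planned contrast needs 84 × 2/(1 + r) per arm: 129, 112 and 99 at r = 0.3, 0.5 and 0.7.

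**If d is on the change-score SD instead (k = 1).** Planned power is 73.1% at every r, against 89.2, 84.5 and 79.8% adjusted.

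**At d = 0.8 (k = 1, r = 0.3).** 99.17 vs 99.97%, a difference of 0.8 points, and less at higher r.

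**Simulation check.** In the same 3,000 trials the mean estimates were 0.394 (planned) and 0.395 (both adjusted forms) for a true 0.40. The variance ratio was 0.748 for ANCOVA and 0.746 for a common baseline mean, against (1 + 0.5125)/2 = 0.756 in theory.

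**The case against.** The strongest reply is that nothing here is an error. The plan openly sets out to compare changes from baseline, and in a randomised trial that contrast is unbiased for these ratings. This stands. A reader might infer that the planned analysis is invalid; the order of events in Section 1.3 A and the simulation both say otherwise.

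The second reply is scope. Section 1.6 B names on-task behaviour, attention and concentration, homework motivation and homework effort as outcomes, all scheduled at every session, and not BAARS, BDEFS or BFIS. Applying the Section 6.1 model to the three ratings is an inference from Section 1.3, since Section 6.1 names no outcomes. This also stands, and it rules out reading the table as power lost on the listed outcomes. For those, averaging 2 baseline and 10 condition sessions (equal correlation assumed) gives a change variance of (1 − r)(1/2 + 1/10) = 0.42 at r = 0.3, and 97.8% power at d = 0.4.

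Third, one might argue that BDEFS deserves special weight because the plan says: "Primary mediation analyses will focus on whether change in the proposed mechanisms of action mediates improvement in AIM total scores and BDEFS". That sentence concerns a separate structural equation model and does not bear on the precision of the efficacy contrast.

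Fourth, the k = 1 figures may flatter the gain. BAARS is the symptom screen (Section 4.1 C), so selection may narrow its baseline spread. A reader might suppose that BDEFS and BFIS escape this, but entry also requires impairing symptoms and a minimum concentration-problem count, which could narrow those scales too. The k = 0.8 rows therefore apply to any of the three. At k = r = 0.7 the gain is nil: 95.0 vs 95.0%.

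Finally, missing post ratings would make the mixed-model estimate differ from the observed change difference. The contrast would still run from arm-specific baselines.

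**Conclusion.** The point holds as one of efficiency, limited to the three-visit ratings and in practice to the d = 0.4 comparisons. On these ratings the planned contrast is never more precise than a baseline-adjusted one, apart from one degree of freedom, and is less precise unless k = r.

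The size depends on quantities the documents do not give. Under the stated assumptions the gain at k = 1 is about 18 power points at r = 0.3, 11 at r = 0.5 and 4 at r = 0.7. At k = 0.8 it is about 10, 4 and less than 1. It is negligible at d = 0.8. The documents do not support a claim of bias, or of a power shortfall on the outcomes listed in Section 1.6 B. The change is worth making because it uses data already scheduled, and because naming the analysis in advance avoids a later choice between change and adjusted results.

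**What to change.** In Section 6.1, Intent to Treat Analysis, state that for BAARS, BDEFS and BFIS the efficacy contrast is adjusted for the initial-evaluation score, by one of two routes:
- a common baseline mean across arms: drop the condition main effect and keep condition by post-baseline time; or
- ANCOVA on the post and 3-month scores, with baseline and baseline-by-time as covariates.

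Optionally add ADHD medication status, the blocking factor, with its time interaction. A constant medication effect cancels in a change contrast, so only the interaction matters there. The gain is minor: 0.3 to 2.9 power points if medicated and unmedicated participants differ by 0.2 to 0.6 SD on change, with 30% to 50% medicated and r = 0.5 (all assumed).

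Do not extend the common-mean constraint to sessions 1 and 2. In the order of Section 1.3 A they follow randomisation, so equal means are not guaranteed by design.

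The cost is a few lines of analysis-plan text and GLIMMIX code, with no new data or participants. With three arms, the common baseline mean saves two parameters; the medication terms, if used, add three over three visits.

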1.0 Research Design

1.1 Purpose/Specific Aims

The study will refine the algorithms that operationalize on-task behavior and the process of displaying participant performance within the virtual reality (VR) environment, then conduct trials to examine said intervention. We will collect data on feasibility, usability and key mechanisms of action, concentration, motivation, and effort/efficiency. A randomized control trial will be implemented to evaluate the effects of the distraction free VR environment alone and combined with automated contingency management and moderators and mediators of outcomes.

A. Objectives

1. Refine objective virtual reality (VR) data capture techniques, including keyboard and mouse click algorithms, eye gaze tracking, and screenshot capturing.
2. Develop and refine contingency management algorithms and conduct focus groups to determine ways to improve feasibility/usability.
3. Pilot test the feasibility/usability of the VR environment and evaluate impact on target mechanisms.
4. Conduct a parallel group randomized trial with college students with ADHD randomized to 1 of 3 groups: (1) VR environment alone, (2) VR + contingency management or (3) a pass-through VR.

B. Hypotheses / Research Question(s)

Data will inform the use of virtual reality to support the academic performance and mental health of individuals with ADHD. The VR intervention will target specific mechanisms of concentration, homework effort, and homework motivation. Trial data will demonstrate the feasibility/usability of the VR system and associated algorithms to monitor attention and focus in VR.

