1.3 Research Design and Methods

The study will take place in 4 phases, each utilizing methodology specific to the phase. Phases are created to improve clarity of expectations for participants entering at different points in the study and clarity of the general research protocol.

- PHASE 1: Refine objective data capture techniques. Key to any VR intervention is the ability to monitor and quantify work productivity behaviors and to establish an accurate baseline. This has been done with adult workers, but we will need to refine the keyboard and mouse click algorithms for use with emerging adults (aged 18-25 years) with ADHD who are completing real homework assignments and studying (n=30 to complete the phase). The study design for this phase will follow an AABBAABB design – where A is passthrough control and B is the immersive VR environment. In this way, each participant essentially serves as their own control as they switch between passthrough and VR immersion sessions. The team will also explore whether adding in eye gaze tracking and periodic screenshots improves the accuracy of the algorithms.
- PHASE 2: Develop and refine contingency management algorithms. Once data capture capabilities have been confirmed in emerging adults with ADHD, we must test the ability to combine these data into an algorithm to provide real-time performance feedback to participants and contingency management (n=30 to complete the phase). As with Phase 1, the study design for this phase will follow an AABBAABB type design – where A is passthrough control and B is the immersive VR environment. In this way, each participant essentially serves as their own control as they switch between passthrough and VR immersion sessions. The team will also conduct focus groups to determine ways to improve feasibility/usability and to identify strategies and tools that motivate participants to complete work.
- PHASE 3: Pilot test and evaluate impact on target mechanisms. Conduct a small randomized control trial (RCT) to assess the feasibility/usability and preliminary effects of the VR environment alone (n=15) compared to VR environment + contingency management (n=15) and the VR passthrough control (n=15). Proposed mechanisms of action will be measured every session,

including algorithm data plus self-ratings of concentration, homework effort, and homework motivation.

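### Choosing mediators for the joint model by single-mediator significance can exaggerate the kept indirect effects and leave real mechanisms out

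*Combined protocol and SAP*

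**What the plan says.** Section 6.1, Mediator Analyses, sets out two stages. In the first, "Preliminary analyses will be conducted separately for each mediator", and "Scores on the mediator will be modeled as a function of pretest scores on the mediator, intervention condition, and covariates"; the other mediators are not listed in that model. The second stage follows from the first, which is to guide a fuller joint model that will "incorporate mediators that emerge as significant within the individual models". Mplus is to estimate "direct and indirect effects using bootstrap estimation procedures". No significance level, multiplicity rule, hold-out sample or repetition of the selection step inside the bootstrap is described. The paragraph closes by naming its target: "Primary mediation analyses will focus on whether change in the proposed mechanisms of action mediates improvement in AIM total scores and BDEFS".

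The candidates are few and fixed in advance. Section 1.1 B names the "specific mechanisms of concentration, homework effort, and homework motivation". Section 1.3, under Phase 3, describes the mechanism measures as "including algorithm data plus self-ratings of concentration, homework effort, and homework motivation". That makes four: objective on-task data, concentration, homework effort and homework motivation.

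**The concern.** A mediator that enters the joint model because it was significant, and is then re-estimated on the same participants, carries a selected estimate. An ordinary bootstrap of the final model does not account for that selection. A real mechanism that just misses significance becomes an omitted variable, and part of its effect passes to whichever kept mediators correlate with it.

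Correlation is the plan's own expectation: for Phase 1, section 6.1 looks for an association above .50 between objective on-task data and self-rated concentration.

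Evaluating mediators is among the aims in section 1.1. What is at stake is which mechanism gets the credit, and how much.

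**Working it through.** **The plan's own figure.** Section 1.5 gives 84 per arm (252 in total), with d = .8 for VR + contingency management against passthrough and d = .4 for the two contrasts involving VR alone. It states no alpha or power, so the 84 cannot be reproduced. Assuming two-sided .05 and a normal approximation, power = Φ(d·√(84/2) − 1.96):

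- d = .4: Φ(2.59 − 1.96) = 73.6%; 80% would need 99 per arm.
- d = .8: Φ(5.18 − 1.96) = 99.9%.

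No power figure is given for mediation.

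**Simulation of the two-stage rule.** Inputs:

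- From the documents: one pairwise contrast with 2 × 84 = 168 participants, and four mediators. The condition-to-mediator effects a = .8 and .4 are borrowed from section 1.5.
- Assumed: a = .2 for weakly moved mechanisms, mediator-to-outcome paths b from 0 to .3, residual correlation rho between mediators, unit residual SDs, no direct effect, and a 95% Monte Carlo interval for a·b in place of the bootstrap.
- Each scenario had 3,000 trials. The true indirect effect is a·b.

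Mediators that passed the single-mediator test entered the joint model. The table gives the mean indirect effect of the first mediator listed, among trials in which it was kept.

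| a of the four mediators | b | rho | True a·b | Mean when kept | Excess |
|---|---|---|---|---|---|
| .8, .8, .8, .8 | .2 | .5 | 0.160 | 0.161 | about 0 |
| .8, .8, .8, .8 | .1 | .5 | 0.080 | 0.091 | +14% |
| .8, .8, .8, .8 | .1 | .3 | 0.080 | 0.111 | +39% |
| .8, .4, .4, .2 | .2 | .5 | 0.160 | 0.223 | +39% |
| .4, .4, .4, .4 | .2 | 0 | 0.080 | 0.114 | +43% |
| .4, .4, .4, .4 | .2 | .5 | 0.080 | 0.106 | +32% |
| .4, .4, .2, .2 | .2 | .5 | 0.080 | 0.139 | +74% |
| .4, .4, .4, .4 | .1 | .3 | 0.040 | 0.077 | +92% |

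A separate run of the last row gave 0.079 (+98%). In the row with two mechanisms at .2, each of those passes in only about 27% of trials. When kept, they average about 0.092 against a true 0.040, an excess of about 130%. In every scenario a model holding all four mediators averaged the true value, within simulation error.

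**Mechanisms lost.** At a = .4 and b = .2, a real mediator is dropped in about 53% of trials at rho = 0 and 25% at rho = .5. At least one of four such mediators is dropped in 52% of trials at rho = .5, and in 87% when two of them have a = .2. With rho = .5, a real mediator with an opposite-sign path (b = −.15, a = .4) is dropped in 73%.

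**Non-mediators passed.** With a = .4 throughout and b = 0, a variable that correlates .5 with a real mediator (b = .3) passes in about 32% of trials, against 3% at rho = 0.

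**Cost of the full model.** For four equally correlated mediators, the variance inflation of each b path is (1 + 2·rho) / [(1 − rho)(1 + 3·rho)].

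- rho = .5: 2 / (0.5 × 2.5) = 1.60, so standard errors grow by √1.60 = 1.26, or 26%.
- rho = .7: 2.4 / (0.3 × 3.1) = 2.58, so √2.58 = 1.61, or 61%.

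**The case against.** Four stronger readings are tempting, and the documents do not support them.

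- **Non-significant mechanisms are barred.** The text says the first stage will guide the second and that significant mediators will be included. It does not say only those, and use of the same data is inferred from silence. The sentence on the primary mediation analyses refers to the proposed mechanisms without restriction. This objection stands as to wording. Significance is still the only entry criterion stated, and no second dataset is mentioned.
- **Correlation pushes mechanisms out.** It does the opposite at the screen: the pass rate of a real mediator (a = .4, b = .2) rises from 47% at rho = 0 to 75% at rho = .5. Losses come from chance, weak treatment effects or opposite-sign paths. Correlation matters afterwards, when kept mediators absorb what was lost.
- **Exaggeration is general.** It is not. If all four mechanisms move by .8 with b = .2 and rho = .5, all are kept in 99.8% of trials and there is no bias.
- **The usual significance-filter factors apply.** These are 1.81, 1.41 and 1.18 at 30%, 50% and 73% power. They describe one z-tested coefficient reported from the test that selected it, not a product of two paths re-estimated in a second model.

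Two further points stand in part. The joint stage removes most of the harm from a passed non-mediator: in the example above, such a variable is significant there in about 4 to 5% of all trials, against about 3% in the full model. And each mechanism does receive an estimate in its own model, though that estimate also carries the effect of correlated mechanisms left out of it.

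**Conclusion.** The concern holds as a possibility whose size depends on unknowns. Followed as written, the rule can overstate the kept indirect effects and omit real mechanisms. The excess runs from about 0, through about +30 to +45% (moved by .4, b = .2), to about +75 to +100% (weaker mechanisms screened out, or b = .1). A weakly moved mechanism that happens to survive can exceed that.

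These figures rest on assumed b and rho, on effect sizes borrowed from the power section and not stated for the mediators, and on a Monte Carlo interval standing in for the bootstrap. The contrasts at d = .4 are the more exposed. The d = .8 contrast is safe only if the mechanisms all move strongly and b is not small.

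A reader might infer that the trial's efficacy result is in doubt. It is not: the intent-to-treat mixed model does not use the mediation screen. This is a worthwhile correction to a supporting analysis.

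**What to change.** In section 6.1, replace the screen with one prespecified parallel-mediator model. It should contain objective on-task data, concentration, homework effort and homework motivation, whatever their single-mediator p-values. Report every specific indirect effect and the total indirect effect with bootstrap intervals. Report the single-mediator models alongside as supporting results; they remain useful if two mechanisms overlap so much that the joint model cannot separate them. If the sponsor prefers to keep a screen, the bootstrap should repeat the whole selection procedure, or selection and estimation should use split samples.

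The change is to wording only and needs no new data; four mediators are feasible with 252 participants. The price is precision on the mediator-to-outcome paths when mechanisms correlate: standard errors about 26% larger at rho = .5 and 61% larger at rho = .7 under equal correlation. The total indirect effect shows what the mechanisms explain jointly when the specific ones are imprecise.
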